5.3 Eligibility Criteria

Consecutive MitraClip patients should be screened per the criteria listed below. Assessment for eligibility criteria is based on medical records of the site and interview with a candidate subject. Subjects must meet ALL of the inclusion criteria to be considered for the clinical study. If ANY of the exclusion criteria are met, the subject is excluded from the clinical study. Consecutive patients meeting these criteria should be asked to provide consent for participation in the EXPAND Study.

5.3.1 Inclusion Criteria

1. Subjects who give consent for study participation
2. Subjects scheduled to receive the MitraClip per the current approved indications for use
3. Subjects with Symptomatic MR ($\geq 3+$)

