2.1.2 MitraClip® Post-Market Clinical Studies

In 2008, based upon data from the EVEREST I study, the MitraClip® received CE mark approval for commercial use in Europe and was indicated for the reconstruction of the insufficient mitral valve for tissue approximation. Clinical evidence generated from EVEREST I, EVEREST II, EVEREST II HRR, and EVEREST II REALISM led to FDA approval in 2013 of the MitraClip® system for the treatment of patients with severe MR who are at prohibitive risk for surgery.

In the time since these approvals, a number of post-market clinical studies have been conducted on the MitraClip. All of these studies have provided continued evidence of the safety and performance of the MitraClip System. The studies for Europe and the US are summarized in the **Table 1**.

Table 1. Summary of Post-Market MitraClip® Studies

Study Reference	Study Design	Study Population	Study Outcome
Franzen et al. ¹⁵ Analysis from Hamburg University Heart Center	Examine MitraClip use in high surgical risk patients not meeting EVEREST criteria	51 subjects 35 (69%) would have been excluded from EVEREST I & II	MitraClip successful in treatment of patients outside of EVEREST criteria
ACCESS-EU ¹⁶ (EU study sponsored by Abbott)	Two-phase prospective, single-arm looking at health economics and clinical	567 subjects 77.1% FMR 84.9% NYHA III or IV High surgical risk	MitraClip implant success 99.6% 78.9 %MR reduction <2+ at 1yr Improved 6MWT, NYHA and QOL ¹⁷
Getting Reduction of Mitral Insufficiency by Percutaneous Clip Implantation GRASP Registry ¹⁸	Prospective Single-center study at Ferrarotto Hospital in Catania, Italy. Site heart team led enrollment criteria	117 high surgical risk 76% FMR 98% MR3+/4+ 63% met EVEREST criteria	100% Acute procedural success Post Procedure MR Reduction 1+ (63%) 2+ (37%) KM Freedom from MAE 96.4% at 30 days and 75.8% at 1 yr
German TRanscatheter Mitral Valve Interventions (TRAMI) Registry	Had both prospective and retrospective enrollment.	828 prospective patients at 21 sites	97% implant success 1.4±0.6 clips/case 85.2% MR reduced to none/ mild Mortality 4.5% 1 m /20.3% 1 yr

¹⁵ Franzen O, Baldus S, Rudolph V, Meyer S, Knap M, Koschyk D, Treede H, Barmeyer A, Schofer J, Costard-Jackle A, Schluter M, Reichenspurner H, Meinertz T. Acute Outcomes of MitraClip Therapy for Mitral Regurgitation in High-Surgical-Risk Patients: Emphasis on Adverse Valve Morphology and Severe Left Ventricular Dysfunction. *Eur Heart J*. 2010; 31:1373-1381.

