2.3.2 Indication for Use

MitraClip® procedures for this study will be conducted in accordance with the Instructions for Use (IFU) that is approved for the region where the implant is taking place.

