9.3 Sample Size Calculations and Assumptions

A sample size of 1000 subjects is expected to adequately capture data on a wide range of subjects with primary or secondary MR, subjects with or without complex valve anatomy, and subjects from Europe and the United States.

[REDACTED]

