The Society of Thoracic Surgeons (STS)/American College of Cardiology (ACC) Transcatheter Valve Therapy (TVT) Registry is a joint initiative of the STS and the ACC. The goals of the registry are to serve as a platform for: 1) device and procedural surveillance; 2) quality assurance and improvement initiatives; and 3) efficient conduct of studies that will speed United States access to new devices and support the expansion of device labeling through evidence development.

Centers that participate in the TVT Registry collect data on demographics, morbidities, functional status, quality of life, hemodynamic status, procedural details, and outcomes (post-operative, 30-day, and 1-year). The ACC National Cardiovascular Data Registry data warehouse and the Duke Clinical Research Institute Data Analysis Center both implement data quality checks, including feedback reports and checks on data range and consistency.

Initial Experience (Nov 2013 – Aug 2014)

The initial experience with commercial transcatheter mitral valve repair in the United States was first published by Sorajja et al.⁵⁶ in 2016. A total of 564 patients were entered into the transcatheter mitral leaflet clip (TMC) module of the TVT registry between November 2013 to August 2014. Approximately 70% of patients were enrolled at centers with pre-commercial experience. Median age of the patients was 83 years, 56% were male. NYHA functional class was III or IV in 86.0%; 292 patients (60.5%) had been hospitalized for heart failure in the year prior to the MitraClip procedure. The median STS-PROM scores for MV repair and MV replacement were 7.9% (IQR: 4.7% to 12.2%) and 10.0% (IQR: 6.3% to 14.5%), respectively.

Consistent with the commercial indication for the MitraClip System, the vast majority (85.5%) of patients had degenerative MR, 9.2% had functional MR, and 5.1% had mixed etiology. However, contrary to the EVEREST studies, implanting physicians were given greater discretion in the treatment of mitral valve

⁵⁵ Tay E, Muda N, Yap J, Muller DW, Santoso T, Walters DL, Liu X, Yamen E, Jansz P, Yip J, Zambahari R, Passage J, Ding ZP, Wang J, Scalia G, Soesanto AM, Yeo KK. The MitraClip Asia-Pacific Registry: Differences in Outcomes between Functional and Degenerative Mitral Regurgitation. *Catheter Cardiovasc Interv.* 2016; 87:E275-281.

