2.0 ANALYSIS CONSIDERATIONS

2.1 Analysis Populations

2.1.1 Analysis Population

2.2 Statistical Methods

2.2.1 **Descriptive Analyses**

Descriptive analysis will be performed to summarize baseline characteristics, acute measures, functional improvement, echocardiographic, clinical measurements, safety and performance measurements. Depending on the type of data (e.g., continuous or categorical), statistical methods described in the following sections will be used.

2.2.1.1 Descriptive Statistics for Continuous Variables

For continuous variables (e.g., age, etc.), results will be summarized as number of observations, means, and standard deviations, and where applicable, with quartiles, minimums, maximums, and 95% confidence intervals for the means. Differences between two groups, where specified, will be summarized with differences of the two means, and 95% confidence intervals for the difference between the means.

A two-sample t-test or Wilcoxon rank sum test, depends on the normality of the data, will be used to test the difference between subgroups. A paired t-test or Wilcoxon sign test will be used to test the difference of measurements between baseline and follow-ups.

2.2.1.2 Descriptive Statistics for Categorical Variables

For binary variables (e.g. gender, APS, etc.), results will be summarized with subject counts and percentages/rates, and where applicable, with exact 95% Clopper-Pearson¹ confidence intervals. Differences between the two groups, when specified, will be summarized with the difference in percent and the Newcombe² score 95% confidence interval for the difference of two percentages.

For endpoints of interest, relative risks (i.e., the ratio of rates), confidence interval for the relative risks, the difference in rates and the confidence interval for difference in rates, and p-values may also be presented for hypothesis generating purposes.

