2.2.3 Logistic Regression

For the univariate analyses, coefficients, Wald's chi-square p-values, odds ratios, and 95% confidence intervals for the odds ratios will be displayed. Note that for variables created from subsets of subjects, only variables with at least 10 subjects in the given subset will be included in this analysis.

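### Entry by regional label associates MR etiology with region, and no visible SAP text adjusts an etiology comparison for region

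*Protocol*

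**What the plan says.** Inclusion criterion 2 (Protocol 5.3.1) takes "Subjects scheduled to receive the MitraClip per the current approved indications for use". Protocol 2.3.2 specifies the "Instructions for Use (IFU) that is approved for the region where the implant is taking place". Protocol 2.1.2 describes the US approval as "for the treatment of patients with severe MR who are at prohibitive risk for surgery". That wording names no etiology. Appendix IV calls the European indication broad. It says of the first US registry report: "Consistent with the commercial indication for the MitraClip System, the vast majority (85.5%) of patients had degenerative MR".

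The sample of 1,000 is justified in Protocol 9.3 and SAP 2.4 as covering "subjects with primary or secondary MR, subjects with or without complex valve anatomy, and subjects from Europe and the United States". The three dimensions are listed side by side, and no link between etiology and region is mentioned.

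For group comparisons, SAP 2.2.1.1 names a two-sample t-test or Wilcoxon rank sum test that "will be used to test the difference between subgroups". SAP 2.2.1.2 gives a difference in percent with a Newcombe interval. SAP 2.2.3 says: "For the univariate analyses, coefficients, Wald's chi-square p-values, odds ratios, and 95% confidence intervals for the odds ratios will be displayed". Protocol 9.4.6 refers the pooling strategy to the SAP, and no visible SAP section takes it up. SAP 2.7 calls the subgroup analyses exploratory and says they will support publication. Its list of subgroups is not visible.

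**The concern.** If etiology is unevenly spread over regions and outcomes also differ by region, a crude FMR versus DMR contrast mixes the etiology effect with the regional difference. A crude Europe versus US contrast has the same fault in reverse. Both conditions are met in the data the protocol cites: the etiology mix differs sharply, and one-year mortality is 15.3% in the eight-country European registry against 25.8% in the US registry.

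The study aims to identify which patients and anatomies suit the new devices (Protocol 1.0 and 2.2). A published crude etiology contrast could therefore mislead on a question that the study sets itself. Pooled rates would also depend on the regional recruitment mix, which the visible text does not fix.

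**Working it through.** **Inputs (Protocol Appendix IV unless stated)**
- European mix: 72.0% FMR (eight-country pilot registry), 77.1% (sponsor's post-approval study), about 70% (German multicentre registry). One German centre had 39-41%.
- US mix (larger registry report): 85.9% DMR; any FMR 17.5%, made up of 8.6% FMR only and 8.9% mixed.
- One-year mortality: Europe FMR 15.0%, DMR 16.2%; US FMR 31.2%, DMR 24.7%.
- European share: not stated. Assumed 50%, range 22-80%. The 220 European XTR subjects (Protocol 3.2) are 22% of 1,000.

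**1. Do the inputs cohere?** Etiology-weighted averages should return the cited overall mortality.
- Europe: 0.72 × 15.0 + 0.28 × 16.2 = 15.3% (cited 15.3%).
- US: 0.825 × 24.7 + 0.175 × 31.2 = 25.8% (cited 25.8%).

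**2. Crude difference, 50% European, mixed counted as FMR.** Cells: Europe 360 FMR, 140 DMR; US 87.5 FMR, 412.5 DMR.
- FMR: (360 × 15.0 + 87.5 × 31.2)/447.5 = 18.2%.
- DMR: (140 × 16.2 + 412.5 × 24.7)/552.5 = 22.5%.
- Difference: -4.4 points (95% CI -9.4 to +0.6).

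**3. Region-stratified difference.** The Mantel-Haenszel weight per region is n(FMR) × n(DMR)/n.
- Europe: 360 × 140/500 = 100.8; difference 15.0 - 16.2 = -1.2.
- US: 87.5 × 412.5/500 = 72.2; difference 31.2 - 24.7 = +6.5.
- Combined: (100.8 × -1.2 + 72.2 × 6.5)/173.0 = +2.0 points (95% CI -4.0 to +8.1).

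**4. Sensitivity (FMR minus DMR, points)**

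| European share | European FMR | US FMR | Crude | Mantel-Haenszel |
|---|---|---|---|---|
| 22% | 72% | 17.5% | -1.5 | +4.3 |
| 50% | 72% | 17.5% | -4.4 | +2.0 |
| 70% | 72% | 17.5% | -4.4 | +0.6 |
| 80% | 72% | 17.5% | -3.9 | 0.0 |
| 50% | 40% | 17.5% | -1.2 | +1.7 |
| 50% | 72% | 8.6% (FMR only) | -5.9 | +1.0 |
| 70% | 72% | 8.6% (FMR only) | -5.2 | -0.1 |

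The FMR-only rows use 85.9% DMR in the US and leave out the remainder. At 50% European, the FMR-only Mantel-Haenszel interval is -5.6 to +7.5.

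**5. Contribution of region alone.** In step 2, Europe supplies 360/447.5 = 80.4% of FMR and 140/552.5 = 25.3% of DMR, an imbalance of 0.551. The regional gap in DMR mortality is 16.2 - 24.7 = -8.5, so region contributes -8.5 × 0.551 = -4.7 points. A true FMR excess of +2 in both regions would appear as -2.7, and one of +4 as -0.7.

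**6. Other endpoints, same split**
- Heart-failure rehospitalization (Europe FMR 25.8%, DMR 12%; US 32.6%, 20.5%): crude 27.1 - 18.3 = +8.8, Mantel-Haenszel +13.1. This is attenuation with no sign change. The cited US overall rate of 20.2% lies below both US etiology rates, so this result needs caution.
- 30-day mortality: (4.5 - 5.2) × 0.551 = about -0.4 points (German and US registries).
- MR 2+ or less: (98.2 - 93.0) × 0.551 = about +2.9 points in favour of FMR. These are post-procedure rates, used because the same sources give no 30-day figures.

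**The case against.** **Missing text.** The subgroup list, the analysis population, the pooling text and possibly a multivariable model are not visible. No visible passage plans an FMR versus DMR test; the visible pre-defined grouping is complex versus non-complex anatomy. This stands as a limit: the point can say only that no adjustment is visible. The SAP's acronym list does define FMR and DMR, which suggests etiology analyses are intended. A region subgroup alone would not adjust an etiology contrast.

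**Aliasing.** A reader might infer that the label makes etiology, region and surgical risk nearly interchangeable. The documents do not support that. The etiology mix is a projection from older registries; the US indication in Protocol 2.1.2 names no etiology; and one European centre had 39-41% FMR. Median predicted surgical mortality was 6.0% in the German registry and 6.1% (for repair) in the US registry.

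**Reversal.** A reader might also infer that crude analysis will reverse the etiology effect. The European stratum is already at -1.2 points (p=0.650), so the reversal is against the region-adjusted average, not against a sign shared by both regions. One row of the table shows no reversal, another gives an adjusted difference of zero, and the adjusted intervals reported in the working all include zero.

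**Choice of inputs.** The German registry had 20.3% one-year mortality. Giving both etiologies that rate, with 70% FMR and a 50% European share, FMR is (350 × 20.3 + 87.5 × 31.2)/437.5 = 22.5% and DMR is (150 × 20.3 + 412.5 × 24.7)/562.5 = 23.5%. The crude gap shrinks to -1.0, yet the strata are then 0 and +6.5. The US etiology-specific rates come from the 63.2% of patients linked to Medicare claims, who tended to be older. The regional gap therefore reflects age and data source as well as the label. It cannot be put down to the label alone, but it confounds a crude contrast whatever its cause.

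**Role of the analyses.** On-label entry is inherent to a post-market study, and the analyses are descriptive and exploratory. That limits the weight of the point. It does not make a confounded contrast safer to publish.

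**Conclusion.** The concern holds as a cheap improvement to the analysis, and it gives no reason to change eligibility. Entry by regional label, together with the cited registries, projects a strong association between etiology and region, and no visible SAP text handles it.

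For one-year mortality, the main illustration gives -4.4 points crude against +2.0 stratified, so the sign can reverse but need not. This rests on an assumed 50% European share, the cited registry rates carrying over to this study, and mixed etiology being counted as FMR. The effect depends on the endpoint: mortality is most exposed, heart-failure rehospitalization is attenuated, and 30-day mortality is little affected. The conclusion is conditional on no region-adjusted method standing in redacted text.

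**What to change.** In SAP 2.2 and 2.7:
- For any etiology comparison, report beside the crude result the within-region results and a region-stratified or region-adjusted estimate: Mantel-Haenszel for rates, region as a covariate in logistic models, and a stratified log-rank test for survival. Include a region-by-etiology interaction.
- Treat region comparisons in the same way, with etiology as the stratum.
- State how mixed etiology is classed, since the result depends on it.
- Show the 30-day safety and performance measures by region and etiology beside the pooled rate.

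If redacted text already does this, no change is needed.

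The cost is SAP wording and one table layout. Intervals will be wide in the small cells: at a 50% European share, 140 European DMR subjects and 43 to 88 US FMR subjects. The sponsor should also confirm that etiology is captured on the eCRF, because the visible baseline and echocardiographic lists (Protocol 6.1.2 and 4.5) do not name it.

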5.3.2 Exclusion Criteria

1. Subjects participating in another clinical study that may impact the follow-up or results of this study.

5.4 Subject Enrollment and Inclusion

The patient is considered enrolled upon signing and dating an informed consent for participation. Consecutive enrolled patients with an attempted MitraClip procedure will be included in the analysis population.

5.5 Subject Discontinuation

Subjects shall remain in the study until completion of the required follow-up period; however, a subject's participation in any clinical study is voluntary and the subject has the right to withdraw at any time without penalty or loss of benefit. Conceivable reasons for discontinuation may include, but not be limited to, the following:

- Subject death
- Subject voluntary withdrawal
- Subject withdrawal by physician as clinically-indicated
- Subject lost-to follow-up as described below

The Sponsor must be notified of the reason(s) for subject discontinuation. The site will provide this information to the Sponsor. Investigators must also report this to their respective IRB/EC as defined by their institution's procedure(s).

No additional follow-up will be required or data recorded from subjects once withdrawn, except for the status (deceased/alive).

Lost-to-Follow-up:

If the subject misses two consecutive scheduled follow up time points and the attempts at contacting the subject detailed below are unsuccessful, then the subject is considered lost to follow-up. Site personnel shall make all reasonable efforts to locate and communicate with the subject (and document these efforts in the source documents), including the following, at each contact time point:

- A minimum of 2 telephone calls on different days over a 30-day period to contact the subject should be recorded in the source documentation, including date, time and initials of site personnel trying to make contact.
- If these attempts are unsuccessful, a letter (certified if applicable) should be sent to the subject.
- If a subject misses one or more non-consecutive follow-up contact time points it will be considered a missed visit. The subject may then return for subsequent visits. If the subject misses two consecutive time points and the above-mentioned attempts at communicating with the subject are unsuccessful, the subject will be considered lost-to-follow-up.

Note: Telephone contact with General Practitioner, non-study cardiologist or relative without presence of subject or indirect documentation obtained via discharge letters will not be considered as subject contact.

5.6 Total Expected Duration of the Study

The time to complete the Study is estimated to be approximately 2 years.

5.7 Expected Duration of Each Subject's Participation

The expected duration of participation for subjects is approximately 12 months.

5.8 Number of Subjects Required to be Included in the Study

Approximately 1,000 subjects will be included for analysis in the Study.

5.9 Estimated Time Needed to Select this Number

The estimated time to include 1,000 analysis patients is about 1 year.

5.10 Study Completion

A Study Completion eCRF must be completed when:

- the subject is considered lost to follow-up per the above definition or
- the subject withdraws from the Study or
- the investigator withdraws the subject from the Study or
- the subject has died or

- upon Study completion (e.g., 1 year follow-up time point has been reached) or
- sponsor termination of Study

Sponsor must be notified of the reason for subject discontinuation. The site will provide this information on the electronic case report form (eCRF). Investigators must also report this to their EC/IRB as defined by their institution's procedure. Subjects will not be replaced.

6.0 TREATMENT AND FOLLOW-UP ASSESSMENTS

6.1 Pre-Treatment

Patients presenting with MR appropriate for treatment with the MitraClip® will undergo screening per standard hospital procedure in accordance with approved labelling. If a MitraClip procedure is considered appropriate (with agreement from local a heart team when required) and the patient meets the screening criteria for the study (i.e. Symptomatic MR \geq 3+ and not participating in another study) the site shall obtain consent from the patient. All efforts should be made by the site to obtain consent from consecutive eligible patients. Echocardiographic verification that there is no evidence of intracardiac, IVC or femoral venous thrombus is required prior to MitraClip procedure per the MitraClip IFU. The MitraClip procedure should be attempted for all consented patients with no evidence of thrombus.

6.1.1 Protocol Required Medications

All medication shall be administered per standard of care procedures for patients that undergo a MitraClip® procedure.

6.1.2 Clinical Assessments

Baseline assessment should be conducted per standard of care. Baseline information to be reported into the study include at minimum: medical history, age, weight, heart rate, blood pressure, history of heart failure hospitalizations, MR severity, and New York Heart Association (NYHA) Functional Class. A baseline QOL conducted by the KCCQ is required to be recorded and submitted for the study. If a 6-minute walk test is conducted as standard of care at baseline, these results will be collected in the EXPAND Study.

6.1.3 Pre-treatment Imaging

Pre-Treatment Transthoracic Echocardiogram (TTE) and Transesophageal Echocardiogram (TEE) should be conducted per standard of care for a MitraClip® Procedure. Copies of all Echocardiograms will be collected by the Sponsor for future reference and may be compared to follow-up echocardiograms.

6.2 Index Procedure

Please refer to IFU for instructions on handling and preparation of the MitraClip® System. All Investigators must read and understand the IFU that accompanies the Device.

6.2.1 Treatment

The MitraClip® procedure should be conducted in accordance with standard of care practice and approved labelling. All consecutive consented patients with an attempted MitraClip procedure will be entered into the study. A procedure is considered attempted when the MitraClip delivery system is introduced.

NOTE FOR U.S. Sites Only: In order to permit device reimbursement, please enter required data into the TVT Registry per your standard processes for all EXPAND Study cases. The data collected in this registry does not replace the data collected by the TVT Registry.

